#### **Phase 3.** Analysis of gut microbiota changes by DNA sequencing after H. pylori eradication therapy and their clinical impact on immunology, metabolism and nutrition

The impact of H. pylori eradication therapy on gut microbiota will be studied by next generation genome sequencing techniques. A comparative analysis will be performed for each therapeutic regimen used. Microbiota changes found will be compared with clinical and analytical data in order to establish their impact on immunology, metabolism and nutrition status at 1 and 12 months post-eradication. Phase 4. Analysis of immunological changes of cell populations, cytokines, chemokines and growth factors after H. pylori eradication therapy and their clinical impact. The impact of H. pylori eradication therapy on humoral and cellular immunity will be studied by flow cytometry and xAMP/Luminex. A comparative analysis will be performed for each therapeutic regimen used. Immunological changes found will be compared with clinical and analytical data in order to establish their clinical impact at 12 months post-eradication.

#### **D.4 Statistical Analysis**

Using the Statistical Package for the Social Sciences (SPSS) version 22.0 (IL, USA). The level of statistical significance will be for a p-value  $< 0.05$ . The normality of data distribution will be evaluated by Kolmogorov-Smirnov or Shapiro-Wilk tests. Continuous variables will be expressed as mean and standard deviation or median and interquartile range and categorical variables as frequency and percentage. The comparison of continuous variables will be made using the Kruskal-Wallis test or Anova test and categorical variables using the Chi-squared test. For the comparison of paired data the Wilcoxon test or Friedman test and the t-Student or Anova test will be used. Further statistical analysis of H. pylori eradication efficacy, gut microbiota and immunological changes is described in Tasks section. The genome sequences will be grouped in OTU according to their similarity. The alpha taxonomic richness and diversity of fecal samples will be expressed in observed species, Sobs index and Shannon index. The composition of fecal

microbiota will be expressed in rarefaction curves and the comparison of the differences in OTU richness with the t-Welch test. Immunological findings will be expressed by radar charts and representative FACS dot-plots. Additional statistical analyses will be defined throughout the study.

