#### Abstract

**Introduction:** Helicobacter pylori (H. pylori) infection remains a major public health problem, with an estimated prevalence of over 50% worldwide and 60-86% for Portugal. H. pylori is associated with significant morbidity and mortality from peptic ulcerative disease to gastric cancer, whose eradication therapy has proven to be effective in preventing these complications. Factors involved in the development of these conditions include H. pylori virulence, host genetic factors and gut microbiota. Given the increasing pattern of antibiotic resistance evidenced by this bacterium and the scarcity of available antibiotic therapy, both in Portugal and worldwide, there is not enough evidence on the best eradication strategy. Regarding the uncertainties about the potential negative impact of indiscriminate use of eradication therapy on gut microbiota, either by proton pump inhibitors or by antibiotics per se, there is an overriding need for evidence about the real impact of this therapy on gut flora and possible clinical consequences in immunological, metabolic, nutritional and oncological terms. **Objectives:** Comparative evaluation of the efficacy of the different quadruple therapy regimens recommended for the H. pylori eradication. Comparative evaluation of the safety profile in terms of clinical, immunological and gut microbiota impact of the different therapies for the H. pylori eradication. **Methods:** Prospective longitudinal multicentre study of total of patients with gastric infection by H. pylori, diagnosed by C-urea breath test or histological analysis of gastric biopsies and clinical indication for its eradication, referred to the different participating Portuguese hospital units and a blind randomized controlled clinical trial of the efficacy and safety of the different quadruple therapy regimes recommended for the H. pylori eradication. This study will be carried out in 4 phases: Phase 1 - Recruitment and randomization of patients by the different quadruple eradication schemes with and without bismuth (5 parallel arms); Phase 2 - H. pylori eradication with evaluation of the efficacy and safety rates at 1 month and the absence of reinfection at 12 months after treatment and collection of stool samples before and after the eradication therapy for evaluation of changes in gut microbiota; Phase 3 - Analysis of richness, diversity and uniformity of gut microbiota by DNA sequencing using the hypervariable region of the ribosomal 16S bacteria gene as a taxonomic identification marker and their clinical impact on immunology, metabolism and nutrition at 12 months after the H. pylori eradication therapy; and Phase 4 - Analysis of immunological changes through the study of cell populations by flow cytometry (CD4+, CD8+, B-cell, T-cell, natural killer cells, cells ratio) and cytokines, chemokines and growth factors by xMAP/Luminex before and 12 months after the H. pylori eradication therapy. **Expected results, impact and scientific outputs:** Given the high rate of triple therapy inefficacy, high antibiotic resistance and the scarcity and controversy of existing literature on quadruple regimens, there may be relevant differences in the approved quadruple regimens for the H. pylori eradication, being necessary to define which is the most effective and safe in Portugal, decreasing the rate of ineffectiveness and exposure to multiple antibiotics. The homeostasis of gut microbiota is significantly changed after H. pylori eradication and this modification may be

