#### **Phase 2.** Eradication of H. pylori and collection of stool and blood samples

Stool samples shall be collected from patients and analyzed on 3 occasions: before (baseline), after stopping treatment (Day 10 or 14) and 1 month after treatment (Day 40 or 44). Blood samples will be collected and analyzed on 2 occasions: before (baseline) and 12 months after treatment. Efficacy and safety rates of H. pylori eradication will be determined for each therapeutic regimen. Carbon 13-labeled urea breath test or upper gastrointestinal endoscopy with biopsies will be performed at 1 month (D40 or D44) and 12 months after treatment. The clinical data, adherence and therapy-related adverse events will be recorded at baseline and during follow-up at 1 and 12 months post-eradication.

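### D.4 names no baseline covariate for comparing regimens on blood immune markers; ANCOVA on a pre-set scale would usually be more precise

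*Combined protocol and SAP*

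**What the plan says.** Section B (Objectives) includes a comparison between regimens of the immunological changes they induce. Section D.3, Phase 4, announces "Analysis of immunological changes of cell populations, cytokines, chemokines and growth factors after H. pylori eradication therapy and their clinical impact", with a comparison by regimen.

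On the data, D.3 Phase 2 says "Blood samples will be collected and analyzed on 2 occasions: before (baseline) and 12 months after treatment". The Abstract agrees: "cytokines, chemokines and growth factors by xMAP/Luminex before and 12 months after the H. pylori eradication therapy". Each patient with both samples therefore has a baseline value for every 12-month marker.

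On the analysis, D.4 says:

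- Between groups: "The comparison of continuous variables will be made using the Kruskal-Wallis test or Anova test".
- Within patients: "For the comparison of paired data the Wilcoxon test or Friedman test and the t-Student or Anova test will be used".
- Distribution: "The normality of data distribution will be evaluated by Kolmogorov-Smirnov or Shapiro-Wilk tests".
- Elsewhere: "Further statistical analysis of H. pylori eradication efficacy, gut microbiota and immunological changes is described in Tasks section". No Tasks section is in the supplied text.
- Later: "Additional statistical analyses will be defined throughout the study".

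The only wording in D.4 specific to immune findings concerns graphical display. D.4 does not name a baseline covariate, a regression model or a transformation. It also does not say whether the variable compared between regimens is the 12-month value or the change.

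**The concern.** In a randomised comparison of a marker measured before and after treatment, the baseline value usually explains part of the spread of the later value. Kruskal-Wallis or ANOVA on 12-month values leaves that part in the error. The same tests on changes subtract the whole baseline, which adds noise unless the two measurements are highly correlated. ANCOVA estimates how much of the baseline to remove.

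This matters because the 46 patients per arm were not derived from any immune-marker difference, and only fairly large differences between regimens can be detected. The baseline blood is already planned, so precision is available without another patient or sample. D.4 also foresees non-normal data, so the scale of any adjusted analysis matters as much as the adjustment.

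**Working it through.** **1. The plan's own sample size.** D.3 gives a prevalence of 86.4%, 95% confidence and a 10% sampling error. n = 1.96² × 0.864 × 0.136 / 0.10² = 45.14, rounded up to 46 per arm; 5 × 46 = 230. The figure reproduces. It is a precision calculation for a prevalence and sets no power for a comparison of regimens.

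**2. Inputs.** From the documents: 46 per arm, five arms, significance at 0.05 (two-sided assumed for pairwise tests), blood at baseline and 12 months. Assumed, because the documents do not give them: the correlation rho, equal SDs at both times, and complete data.

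**3. Variance of a between-arm contrast**, with the 12-month-value analysis set to 1:

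- changes: 2(1 − rho)
- ANCOVA: 1 − rho²
- ANCOVA relative to changes: (1 − rho²) / [2(1 − rho)] = (1 + rho)/2

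| rho | ANCOVA / values | cut | ANCOVA / changes | cut |
|---|---|---|---|---|
| 0.1 | 0.99 | 1% | 0.55 | 45% |
| 0.3 | 0.91 | 9% | 0.65 | 35% |
| 0.5 | 0.75 | 25% | 0.75 | 25% |
| 0.7 | 0.51 | 49% | 0.85 | 15% |
| 0.9 | 0.19 | 81% | 0.95 | 5% |

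Estimating the slope costs a factor of about 1 + 1/(N − k − 2) = 1 + 1/223, with N = 230 and k = 5. With it, the ratio to values is 1.002 at rho 0.05 and 0.9996 at 0.07. The ratio to changes is 0.994 at rho 0.98 and 0.9995 at 0.99. So there is no gain over values below rho of about 0.07, and almost none over changes from about 0.98.

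**4. Detectable difference.** Five-arm omnibus F test, one regimen differing from the other four by d SD, 80% power, 4 and 225 degrees of freedom (224 for ANCOVA). The noncentrality is 46 × 0.8 × d² / v, where v is the relative variance from step 3. For values (v = 1) the solution is d = 0.576.

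| rho | values | changes | ANCOVA |
|---|---|---|---|
| 0.3 | 0.58 | 0.68 | 0.55 |
| 0.5 | 0.58 | 0.58 | 0.50 |
| 0.7 | 0.58 | 0.45 | 0.41 |

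**5. Skewed markers.** Simulated power for lognormal markers (log SD 1, 46 per arm, one arm shifted by 0.5 log-SD, 21,000 trials per rho):

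| rho | Kruskal-Wallis, raw change | Kruskal-Wallis, values | raw ANCOVA | rank ANCOVA | log ANCOVA |
|---|---|---|---|---|---|
| 0.3 | 0.47 | 0.63 | 0.53 | 0.68 | 0.71 |
| 0.5 | 0.61 | 0.63 | 0.59 | 0.77 | 0.80 |
| 0.7 | 0.84 | 0.64 | 0.72 | 0.91 | 0.94 |

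On the raw scale, ANCOVA is beaten by Kruskal-Wallis on values at rho 0.3 and 0.5, and by Kruskal-Wallis on changes at 0.5 and 0.7. In null simulations (rho 0 to 0.9) the type I error was 0.047 to 0.055 for log ANCOVA and 0.046 to 0.053 for rank ANCOVA.

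**6. Where the gain fails or shrinks** (smaller simulations, 46 per arm, one arm shifted):

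- High rho, lognormal marker: Kruskal-Wallis on log change beats rank ANCOVA, with power 0.76 v 0.72 at rho 0.9, 0.86 v 0.84 at 0.95 and 0.80 v 0.74 at 0.98. Compare within each rho only.
- Logged marker still heavy-tailed (t with 2 degrees of freedom, rho 0.3, shift 0.6): over two runs, log ANCOVA had power 0.20 to 0.21 against 0.46 to 0.52 for Kruskal-Wallis on values. Rank ANCOVA had 0.50 in the run where Kruskal-Wallis had 0.46.
- Half the values at a floor: rank ANCOVA 0.62 v 0.58 for Kruskal-Wallis on values at rho 0.3, and 0.67 v 0.57 at rho 0.5.

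**The case against.** The strongest objection is that the deciding text may be in the Tasks section, to which D.4 refers for this very topic. The Kruskal-Wallis/ANOVA sentence is a general line for all continuous variables, and D.4 leaves further analyses open. This stands: a reader might infer that the trial has no baseline-adjusted immune analysis, but the supplied text cannot show that. The request must be conditional.

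Second, the ANOVA listed for paired data could be a repeated-measures ANOVA with a regimen-by-time term. That reading is fair, and it means baseline need not be ignored. With two time points, however, that test is the comparison of changes, so the changes columns above already cover it.

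Third, the size rests on an assumed rho. At rho 0.3 the detectable difference against 12-month values moves only from 0.58 to 0.55 SD. This stands as a limit on the size. It does not remove the point, because the larger gains against changes occur at low rho, and the objectives and Phase 4 lean towards changes.

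Fourth, no form of ANCOVA wins everywhere. Step 6 confirms this, and a bare instruction to use ANCOVA would be poor advice. A rank-scale difference is also not in marker units, so it gives no usable effect estimate.

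**Conclusion.** The point holds as one of precision. In the supplied text, D.4 names only tests without a baseline covariate for comparing regimens on the blood immune markers. A reader might infer that these comparisons would be biased or invalid; the documents do not support that, because allocation is randomised and the named tests remain valid.

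For assumed rho of 0.3 to 0.7, equal SDs and complete data, ANCOVA on a suitable scale cuts the between-arm variance by 35% to 15% against changes and by 9% to 49% against 12-month values. The gain is negligible for rho near 0 (against values) or near 1 (against changes). It is not guaranteed for rank ANCOVA at rho of about 0.9 or more, or for log ANCOVA when the logged marker is still heavy-tailed. Confidence is medium, because the Tasks section was not available and rho is unknown.

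**What to change.** If the Tasks section already specifies baseline adjustment for the immune comparisons, cite it in D.4. Otherwise add to D.4:

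- **Model.** Compare regimens on each immune marker by ANCOVA, with the 12-month value as outcome, regimen as factor and the baseline value as covariate.
- **Scale.** Fix it in advance per marker type, without looking at results by arm. Use the log scale for positive, skewed concentrations. Use rank ANCOVA, for the test only, where many values sit at a detection limit or the logged values remain heavy-tailed. Do not use raw-scale ANCOVA on skewed markers.
- **Reporting.** For markers on the log or raw scale, give adjusted ratios or differences with 95% CIs. For rank-analysed markers, give the p-value with medians and interquartile ranges by arm.
- **Missing baseline.** Fill it with the overall baseline mean, so that patients with a 12-month sample stay in the comparison.
- **Within-arm tests.** Treat before-after tests within an arm as descriptive.

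The cost is one error degree of freedom (224 instead of 225), plus writing the scale rule and the missing-baseline rule beforehand and doing the blinded checks that the scale rule needs. No extra patient, visit or sample is required.

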### **B. Objectives**

- To determine and compare the efficacy of the different therapeutic regimens recommended as *H. pylori* eradication therapy;
- Comparative evaluation of the safety profile in terms of clinical, immunological and gut microbiota impact of the different recommended therapies for the *H. pylori* eradication:
- To evaluate the changes in gut microbiota after the *H. pylori* eradication therapy;
- Compare the changes in gut microbiota induced by the different therapeutic regimens for *H. pylori* eradication and evaluate their clinical implications on immunology, nutrition and metabolism;
- To evaluate the immunological changes after the *H. pylori* eradication therapy;
- Compare the immunological changes induced by the different therapeutic regimens for *H. pylori* eradication and evaluate their clinical implications.

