surgery or neoplasia; Previous H. pylori eradication therapies; Antibiotic or probiotic therapies in the month prior to recruitment; Use of proton pump inhibitors, other antacids or gastric mucosal protection agents in the 2 weeks prior to recruitment; Corticosteroids or immunomodulatory therapy in the month prior to recruitment; Immunodeficiency; Insulin-treated diabetes mellitus; Obesity (Body mass index  $\geq 30\text{Kg/m}^2$ ); Use of laxative therapy in the 15 days prior to recruitment; Decompensated heart, liver, kidney or respiratory diseases and; Refusal or inability to give informed consent. H. pylori eradication schemes: Each patient will randomly follow one of the five H. pylori eradication schemes (5 parallel arms): sequential, hybrid, concomitant with bismuth and two concomitants bismuth-free. Sample size calculation: Assuming the estimated prevalence of H. pylori gastric infection in Portugal in adults is 86.4%, it was determined that for a 95% confidence level and a 10% sampling error it will be necessary to include 46 patients in each of the 5 arms of the study, making a total of 230 patients.

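### OTU richness is assigned a two-sample Welch test, although the objective is a five-arm comparison of change with a baseline stool sample; a baseline-adjusted five-arm model with a stated multiplicity rule would serve it better

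*Combined protocol and SAP*

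**What the plan says.** D.4 Statistical Analysis ties one test by name to OTU richness: "the comparison of the differences in OTU richness with the t-Welch test". It does not say which groups or time points are compared, or whether the samples are paired.

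The same section gives two general rules. One covers group comparisons: "The comparison of continuous variables will be made using the Kruskal-Wallis test or Anova test and categorical variables using the Chi-squared test". The other covers repeated samples: "For the comparison of paired data the Wilcoxon test or Friedman test and the t-Student or Anova test will be used". Neither is linked to microbiota or to a between-arm comparison of change. D.4 sets significance at p < 0.05, states no multiplicity rule, and points elsewhere for detail: "Further statistical analysis of H. pylori eradication efficacy, gut microbiota and immunological changes is described in Tasks section". The Tasks section is not in the supplied text.

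The design and aims are clear:
- B. Objectives: "Compare the changes in gut microbiota induced by the different therapeutic regimens".
- D.3, Phase 1: "it will be necessary to include 46 patients in each of the 5 arms of the study".
- D.3, Phase 2: "Stool samples shall be collected from patients and analyzed on 3 occasions", namely baseline, end of treatment (Day 10 or 14) and one month after treatment (Day 40 or 44).
- D.3, Phase 3: "A comparative analysis will be performed for each therapeutic regimen used", with no test named.

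**The concern.** The test named for richness does not match the question. Comparing change across five regimens needs a multi-arm analysis that uses the baseline sample. A two-sample test gives neither unless it is applied pair by pair, and it uses baseline only if the variable tested is a change score, which D.4 does not say.

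Two things are at stake. Pairwise testing without a rule raises the chance of declaring a difference between regimens that does not exist. Analysing post-treatment values alone gives up precision that the baseline sample, already planned for every patient, could supply. The second is a loss of power and not a bias, because the arms are randomised.

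**Working it through.** **Inputs.** From the documents: 5 arms, 46 patients per arm, one baseline and two post-treatment stool samples, two-group Welch test, p < 0.05. Assumed, because the documents give no SD, correlation or dropout: normal data, all 46 patients per arm analysed, two-sided tests, correlation r = 0.3, 0.5 or 0.7 between samples from one patient, and a difference of 0.5 SD for power.

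**Step 1. The plan's own figure.** The precision formula for one proportion gives n = 1.96² × 0.864 × 0.136 / 0.10² = 45.14, rounded up to 46; 5 × 46 = 230. Both stated figures reproduce. They describe the precision of a prevalence and imply no power for richness.

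**Step 2. Number of comparisons.** Five arms give 5 × 4 / 2 = 10 pairs per time point.

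**Step 3. False positives at one time point** (simulation, 20,000 runs, 46 per arm).

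| Procedure | True state | Chance of at least one false difference |
|---|---|---|
| 10 unadjusted tests, no global test | all arms identical | about 28% (28–29% across runs) |
| Global ANOVA first, then unadjusted pairs | all arms identical | about 5% |
| Global ANOVA first, then unadjusted pairs, post-treatment values | one arm shifted by 0.5 to 1.0 SD | 18–21%, among the four identical arms |
| Tukey contrasts, baseline as covariate | all arms identical | about 5% |
| Tukey contrasts, baseline as covariate | one arm shifted by 0.5 or 1.0 SD | about 3%, among the four identical arms |

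A global test alone therefore controls the error only when no arm differs.

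**Step 4. Precision from baseline.** Relative to a post-treatment value with variance 1, a change score has variance 2(1 − r) and a baseline-adjusted value 1 − r². Effective n is 46 divided by that factor.

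| | r = 0.3 | r = 0.5 | r = 0.7 |
|---|---|---|---|
| Post-treatment value alone | 46 | 46 | 46 |
| Change score | 46/1.4 = 33 | 46/1.0 = 46 | 46/0.6 = 77 |
| Baseline as covariate | 46/0.91 = 51 | 46/0.75 = 61 | 46/0.51 = 90 |

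**Step 5. Power for one pair at 0.5 SD.** The noncentrality is 0.5 / √(2v/46), where v is the variance factor. For v = 1 it is 2.40, which gives 66%.

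| | r = 0.3 | r = 0.5 | r = 0.7 |
|---|---|---|---|
| Post-treatment value, single test | 66% | 66% | 66% |
| Change score, single test | 52% | 66% | 86% |
| Baseline as covariate, single test | 70% | 78% | 91% |
| Post-treatment value, Tukey (critical t 2.75) | 36% | 36% | 36% |
| Baseline as covariate, Tukey | 41% | 51% | 73% |

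At the same Tukey threshold, baseline adjustment always helps. Set against one unprotected test on post-treatment values (66%), it fully offsets the stricter threshold only at r = 0.7. The adjusted figures are for ANCOVA at one time point, taken as an approximation to the mixed-model contrast at that time.

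**Step 6. Multiplicity beyond one time point.** With identical arms, baseline-adjusted Tukey applied separately at each time gives a familywise error of about 9–10% over the two post-treatment times. Over two times and two indices (richness and Shannon) it is about 14–18%, assuming a correlation of 0.5 or 0.8 between the indices (6,000 runs). A sound rule must therefore also name the time point and the index.

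**The case against.** The strongest reply is that D.4 already lists tests that can handle the design. Kruskal-Wallis and ANOVA accept five arms and could be run on change scores, and a general rule need not be repeated for each variable. This stands in part: a reader might infer that the plan contains no test capable of a five-arm comparison, and that is not so. But a specific sentence on richness sits beside the general rule and points to a different test. Nothing says which governs, what form the outcome takes, or which time point counts.

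A reader might also infer that Welch will be run on before-and-after samples as if they were independent. The documents do not support that, because it would contradict D.4's own rule for paired data.

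The 28% figure is conditional. It needs ten unadjusted tests with no global test first, and no section states that procedure. Nor does any section state a global test followed by unadjusted pairs.

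Finally, the Tasks section is cited for exactly this subject and may supply the missing detail. That stands as a limit on the finding. It does not rescue the Welch sentence, which would then be at odds with the fuller plan or redundant.

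**Conclusion.** The point holds as a mismatch between the test named for richness and the stated comparison. The supplied text assigns no multi-arm test, baseline adjustment or multiplicity rule to the comparison of microbiota change between regimens, and a better method is available from samples already planned.

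The gain in effective n, from 46 to about 51, 61 or 90 per arm, depends on a correlation that the documents do not give. At r = 0.3 it is small (single-pair power 66% to 70%). The multiplicity risk is about 28% at one time point at worst, and about 5% with a global ANOVA first if all arms are identical.

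It does not follow that the trial lacks such an analysis, since the Tasks section could not be seen. Nor does it follow that Welch tests between arms would be invalid or biased: each single test would be sound. The change is one the sponsor should make. Confidence is medium, because of the unseen section and the assumed correlations.

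**What to change.** In D.4, replace the Welch sentence with the following:
- **Model.** Post-treatment richness modelled on arm (five levels), time (Day 10/14 and Day 40/44), arm-by-time and the baseline value, with a patient random effect. ANCOVA at one named time point is an acceptable simpler form.
- **Confirmatory comparison.** Name one time point and one index, for example richness at Day 40/44. Test arm globally there, then report Tukey-adjusted pairwise differences with confidence intervals.
- **Exploratory.** Label the other time point and the Shannon index as exploratory.
- **Distribution.** Transform, or use ranks, if the planned normality check fails.
- **Before/after change.** Keep the listed paired tests for this purpose.

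If the Tasks section already specifies such a model, cite it in D.4 and delete the Welch sentence.

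The cost is a change of wording and slightly more analysis work, with no new samples. The downside is the stricter pairwise threshold: Tukey power for 0.5 SD is 41%, 51% and 73% at r = 0.3, 0.5 and 0.7.
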